8.2 Visual analog scale (VAS)

The VAS is a validated commonly used pain score. A copy of the VAS score is provided in Appendix E.

*8.3 Patient-reported outcomes (PRO) and patient global impression of change (PGIC)* The patient-reported outcomes (PRO) and patient global impression of change (PGIC) questionnaire is provided in Appendix G.

## 9. Statistical Analysis

#### Safety Analyses

Cumulative rates of AEs will be estimated and 95% CIs will be reported. AEs will be analyzed as a composite of all AEs, composites based on major AE types or severity and as individual AE types. The rates will be compared qualitatively to values reported in the literature of other studies of GAE and knee arthroplasty. An interim safety analysis will be performed after the first 10 patients are treated.

With 40 patients expected with the stratification of moderate and severe arthritis, we can achieve approximate 83% power to test the difference of 10% of the upper bound of a 95% CI for an AE rate of <0.01% (no such events seen) vs 10%. At this sample size, for AE rates of 0% to 50%, the difference between the upper bound of the 95% CI and the estimate AE rate ranges from 7.1% to 14.8%. These calculations were based on exact binomial CIs, assuming no loss to follow up.

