## Rationale

The knee receives its blood supply from the genicular arteries, branches from the superficial femoral and popliteal arteries. Deliberate partial blockage of the genicular arteries (embolization) leads to reduction of the inflammatory response, with potential improvement in pain. Recently, Okuno and colleagues reported their experience with genicular artery embolization for patients with mild-to-moderate knee osteoarthritis. In their pilot study, 14 patients underwent embolization (7). No major adverse events were reported. There was a dramatic and rapid reduction in symptom and pain scores of patients.

In 2017, the same authors reported their results of genicular artery embolization performed on 95 knees in 72 patients (6). All patients had pain that was resistant to conservative treatment, such as oral nonsteroidal ant-inflammatory drugs, oral opioid agents, physical therapy, stretching, muscle strengthening, or intraarticular injection of hyaluronic acid. The distribution of local tenderness (indicating the presence of inflammation) was evaluated in all cases immediately before transcatheter arterial embolization and subdivided into eight areas to determine the key arteries to be treated. After selective catheterization of the appropriate genicular artery, imipenem/cilastatin sodium was used as the embolic material in 88 knees in 65 patients. Patients who had contraindications to imipenem/cilastatin (ie, a history of hypersensitivity or allergy to antibiotic agents or treatment with valproic acid) were treated with 75-µm Embozene microspheres instead (7 knees in seven patients).

Mean Western Ontario and McMaster Universities Osteoarthritis Index (WOMAC) pain scores decreased significantly from 12.1 at baseline to 6.2 at 1 month, 4.4 at 4 months, 3.7 at 6 months, 3.0 at 12 months, and 2.6 at 24 months after the first transcatheter arterial embolization procedure (all P < .001). The intent-to-treat clinical success rate at 6 months of follow-up was 86.3% (95% CI, 78%–92%). The mean total WOMAC score also decreased significantly from 43 at baseline to 24, 14.8, 11.2, 8.2, and 6.2 at 1, 4, 6, 12, and 24 months, respectively (all P < .001). The mean VAS score significantly decreased from 72 at baseline to 38, 29, 19, 13, and 14 at 1, 4, 6, 12, and 24 months, respectively (all P < .001). Patients reported a decrease in the dose of medication used and frequency of other treatments after the procedure.

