No serious adverse events were noted. Minor complications occurred, such as moderate subcutaneous hemorrhage at the puncture site and transient cutaneous color change on the treated knee, all of which resolved without treatment.

While these single center results show a great deal of promise, the vast majority of patients underwent embolization with imipenem/cilastatin, which is not readily available in the United States. Seven patients underwent embolization with small calibrated microspheres (75- $\mu$ m Embozene, Boston Scientific). While equivalent success rates were shown between the two embolics, the low number of patients treated with Embozene microspheres precludes a true comparative analysis.

Embozene particles are FDA approved for the embolization of hypervascular tumors and arteriovenous malformations. Several studies have shown excellent safety and efficacy with regards to tumor control and objective response in liver cancer (13, 14). It has been used extensively for the treatment of symptomatic uterine fibroids, where Embozene embolization of the uterine arteries results in necrosis of uterine fibroids and cessation of abnormal vaginal bleeding (9). Other proven uses include embolization of arteriovenous malformations and fistulas (15).

Genicular artery embolization appears to be safe and effective for the treatment of knee osteoarthritis based on a single center study. Its mechanism of action in decreasing knee hypervascularity and inflammation appears consistent with other studies. Embozene particles are FDA-approved for the treatment of hypervascular tumors, and have shown promise in this arena. Based on these principles, a study of the safety and efficacy of Embozene particles for genicular artery embolization is warranted.

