# 5.1 Visit 1: Screening/Baseline (within 8 weeks of GAE)

Subjects that meet all eligibility criteria listed in Section 3 above are eligible for participation in this study.

Prior to enrollment, each patient will have the following assessments performed:

- Obtain written informed consent
- Medical history, including demographics
- Physical examination including vital signs
- Western Ontario and McMaster Universities Osteoarthritis Index (WOMAC, version 3.1) questionnaire
- Visual analog scale (VAS) score
- Laboratory evaluation: serum complete blood count and basic metabolic panel
- Knee MRI without contrast. If patients cannot undergo MRI (e.g. pacemaker, significant claustrophobia), then CT of the knee without contrast will be performed. If a knee MRI or CT has already been performed within 6 months of Visit 1, that will be accepted.
- Knee x-ray (within 6 months of Visit 1)
- Evaluation for moderate sedation

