# 6. Withdrawal of Subjects

Subjects will be informed that they have the right to withdraw from the study at any time for any reason, without prejudice to their medical care. The Investigator also has the right to withdraw patients from the study for any of the following reasons:

- Adverse Event
- Concurrent medical condition
- Patient unwillingness to comply with study requirements
- Patient death
- Other Investigator decision

If a patient is withdrawn or discontinued from the study, the reason for withdrawal will be recorded in the source documents and on the End of Study case report form (CRF). All patients withdrawn from the study will be encouraged to complete, if possible, all clinical evaluations scheduled for the 12-month follow-up visit. All adverse events will be followed as described in Section 7. Patients who are withdrawn from the study for any reason will not be replaced. The Principle Investigator may terminate the study at any time.

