# 7. Adverse Events

# 7.1 Definitions

Adverse Event: An adverse event (AE) is any untoward medical occurrence in a patient regardless of any causal relationship with a study treatment or procedure. An AE can therefore be any unfavorable or unintended sign, symptom, or disease temporally associated with the use of a medicine or a procedure, whether or not considered related to the product or procedure. A non-serious AE is any untoward medical occurrence that does not meet any of the criteria for a serious adverse event as defined below.

Laboratory data will be collected as described in this protocol. Clinical syndromes associated with laboratory abnormalities are to be recorded as appropriate.

Patients will be instructed to report AE that they experience to the Investigator or Study Coordinator at each visit. AEs occurring during the trial and the protocol-defined 12-month follow-up period will be reported on the AE case report form (CRF). The Investigator will record AE terms according to Medical Dictionary for Regulatory Activities (MedDRA) lowest level terms. Whenever possible, a specific disease or syndrome will be reported rather than the associated signs and symptoms. Independent signs and symptoms will be reported as separate AEs.

All AEs will be assessed for severity, relationship to the study treatment, treatment required and outcome/resolution. This information will be reported on the AE CRF.

Serious Adverse Event: A serious adverse event (SAE) is any AE, occurring at any dose and regardless of causality, that:

- Results in death
- Is life-threatening, such that the patient was at immediate risk of death from the event as it occurred
- Requires inpatient hospitalization or prolongation of existing hospitalization; note that hospital admissions and/or surgical operations scheduled to occur during the study period but planned prior to study entry are not considered AEs if the illness or disease was diagnosed before the patient was enrolled in the study (provided that the patient's condition does not deteriorate in an unexpected manner during the study)
- Results in persistent or significant disability or incapacity, such that the patient experiences a substantial disruption of their ability to perform normal functions

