#### 7.2 Adverse Event Reporting

The Investigators are responsible for monitoring the safety of patients who have been enrolled in the study. All AEs considered to be related to the procedure or study device will be followed until the event resolves or has reached a fatal outcome. AEs will be evaluated for severity using the standardized terms "mild," "moderate" and "severe."

The Investigators will document all AEs occurring during the study, commencing with the date of the GAE treatment and including the protocol-defined 12-month follow-up period. AEs and SAEs that occur following the signature of informed consent but prior to treatment will not be captured or reported.

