#### 7.3 Serious Adverse Event Reporting

Any unanticipated SAE, including death due to any cause that occurs during the study treatment or initial 12-month follow-up period, related to the procedure or study device, will be reported to the FDA within 3 days of the site learning of the event.

Unrelated SAEs will be reported at the FDA IDE annual report. The SAE must be completely described on the AE CRF as well as the Serious Adverse Event Form.

All safety concerns should be reported to:

[name] [name] [contact] [contact]

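### The only safety look tied to enrolment is triggered by treating patient 10, has no minimum follow-up, decision criterion or stated consequence, and is not repeated for patients 11 to 40

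*Combined protocol and SAP*

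**What the plan says.** All references are to the combined protocol and SAP. Section 2.1 makes safety the primary objective. Section 4 sets 40 patients, one arm, one centre and 12 months of follow-up.

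Section 9 (Safety Analyses) gives the interim one sentence: "An interim safety analysis will be performed after the first 10 patients are treated". The same paragraph says that adverse events (AEs) will be analysed as an overall composite, as composites by major type or severity, and as individual types, with 95% confidence intervals and a qualitative comparison with the literature. It does not link any of these to the interim.

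The other safeguards in the visible text are:

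- **Section 5.3:** AE review at every follow-up visit, and knee MRI or CT at Month 3. Section 7.4 gives detection of non-target embolization as the purpose of that imaging.
- **Section 6:** "The Principle Investigator may terminate the study at any time".
- **Section 7.1:** "All AEs will be assessed for severity, relationship to the study treatment, treatment required and outcome/resolution".
- **Section 7.2:** "The Investigators are responsible for monitoring the safety of patients who have been enrolled in the study".
- **Section 7.3:** unanticipated serious AEs related to the procedure or device "will be reported to the FDA within 3 days of the site learning of the event".
- **Sections 12 and 13:** conduct under ICH E6 and applicable regulation, and safety updates to the IRB.

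Section 10 covers the accuracy and completeness of data and names no safety reviewer.

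**The concern.** The look is defined by a count of treated patients. Followed to the letter, it can be done on the day patient 10 is treated, before that patient has any follow-up visit and before the Month 3 imaging of the most recent patients. Nothing says which result would matter or what would follow from it. The remaining 30 patients are then treated with no further look tied to enrolment.

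The existing safeguards do not close this gap. Section 6 permits termination and sets no condition for it. Sections 7.3 and 13 impose reporting. The three-day FDA report covers unanticipated related events. A build-up of anticipated harms, such as the osteonecrosis and skin or toe necrosis listed in Section 7.4, has no stated trigger.

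The prior data in the Rationale do not make a rule unnecessary. The larger series covered "genicular artery embolization performed on 95 knees in 72 patients", and "No serious adverse events were noted". Only 7 of those patients received Embozene, at 75 micron. This study uses 100 micron.

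**Working it through.** **The plan's own figures.** Section 9 gives none for the interim. Its power of about 83% and its 7.1% to 14.8% distance to the upper bound refer to all 40 patients. The distances do not reproduce with exact two-sided limits: 0/40 gives 1 − 0.025^(1/40) = 8.8%, and 20/40 gives 16.2%. That is a separate matter, and nothing below uses those figures.

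**What the prior data and a clean look exclude.** The upper exact 95% limit for 0 events in n is 1 − 0.025^(1/n).

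- 0/72 serious AEs: 5.0%. Of these 72 patients, 65 received another embolic.
- 0/7 with Embozene: 41.0%.
- 0/10 at the interim: 30.8%.
- Chance of no event in 10: 0.9^10 = 34.9% at a true 10%, and 0.8^10 = 10.7% at a true 20%.

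**Illustrative boundaries.** The tolerable rate is an assumption that the sponsor must set. The boundary at each look is the smallest count whose one-sided 95% Clopper-Pearson lower limit exceeds that rate. For 3%: 2/10 has lower limit 3.7% (1/10: 0.5%), 3/20 has 4.2% (2/20: 1.8%), and 4/30 has 4.7% (3/30: 2.8%).

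**Chance of a pause, 3% rule, true rate 20%, all events known.** In 10 patients, P(0) = 0.1074, P(1) = 0.2684, P(2) = 0.3020, P(≥2) = 0.6242, P(≥3) = 0.3222 and P(≥4) = 0.1209.

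- Look at 10: 0.6242.
- Look at 20: 0.1074 × 0.3222 + 0.2684 × 0.6242 = 0.2021.
- Still running after 20 with a total of 0, 1 or 2: 0.0115, 0.0577, 0.1045.
- Look at 30: 0.0115 × 0.1209 + 0.0577 × 0.3222 + 0.1045 × 0.6242 = 0.0852.
- Sum: 0.6242 + 0.2021 + 0.0852 = 0.9115, printed as 91.2% after rounding the unrounded terms.

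The same recursion gives the chance of a pause over three looks:

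| Tolerable rate | Boundaries | True 5% | True 10% | True 20% | True 30% |
|---|---|---|---|---|---|
| 3% | 2/10, 3/20, 4/30 | 13.7% | 46.9% | 91.2% | 99.4% |
| 5% | 3/10, 4/20, 5/30 | 2.9% | 22.2% | 77.6% | 97.5% |
| 10% | 4/10, 5/20, 7/30 | 0.3% | 5.6% | 47.7% | 87.5% |

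**Incomplete knowledge at the look, true rate 20%.** The documents give no accrual rate, so both lines are assumptions.

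- Half of the latest cohort's events known, earlier cohorts complete: 80.2%, 60.3% and 27.2% (3%, 5%, 10% rule).
- Half of all events known: the visible rate is 0.5 × 20% = 10%, so the true-10% column applies, giving 46.9%, 22.2% and 5.6%.

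**Unneeded pause when the true rate equals the tolerable rate.** Three looks give 4.8%, 2.9% and 5.6%. If the 30-patient count is also carried through patients 31 to 40, add the chance of first reaching it there. For the 3% rule, the chances of totals 0, 1, 2 and 3 after look three are 0.4010, 0.3721, 0.1496 and 0.0293. The addition is 0.4010 × 0.0001 + 0.3721 × 0.0028 + 0.1496 × 0.0345 + 0.0293 × 0.2626 = 0.014, giving 6.2%. The same step adds 2.8 points for the 5% rule (5.7%) and 6.0 points for the 10% rule (11.6%). The death trigger is not included in any of these figures.

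**Length of a hold.** Section 4 puts the Week 1 visit at 7 ± 4 days, which is 3 to 11 days; three holds take at most 33 days. One hold uses up to 11 of the 56 days in the Section 5.1 baseline window (20%).

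**The case against.** A reader might infer that the interim has no content. That goes too far. The sentence closes a paragraph that lists the AE composites and intervals, and the natural reading is that these are tabulated for the first 10 patients. What is missing is a prioritised event, a threshold, a minimum follow-up and a consequence.

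A reader might also infer that safety goes unwatched after patient 10. The documents do not support that either. Treatment is open at one centre, AEs are reviewed at each visit, the investigators are responsible for safety monitoring, and the study can be stopped at any time. One related toe necrosis could end it. Under the example rules, by contrast, 2 of 10 patients (5% rule) or 3 of 10 (10% rule) would not force a pause. This objection stands as far as it goes: a count rule can only be a floor beneath discretion.

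The third tempting reading is that the pause probabilities measure an improvement over the plan. They do not. Applied at 10 patients only, the same boundaries pause 62.4%, 32.2% or 12.1% of the time at a true 20% (3%, 5%, 10% rule), but the plan contains no such boundaries. The comparison shows the effect of adding looks under one rule and says nothing about how discretion would perform.

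Two further points stand. The 5% illustration matches an upper limit drawn mostly from another embolic and from a different event definition. Week 1 holds will also miss late events, so completeness depends on accrual.

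Finally, the Appendix B flow chart and the Appendix F device instructions cannot be seen here, one passage was removed, and FDA conditions on the device exemption may exist outside this text.

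**Conclusion.** The point holds for the visible text. One enrolment-linked look, triggered by treatment, serves the primary objective. It can precede patient 10's first follow-up visit, carries no decision criterion or consequence, and is not repeated for 30 of the 40 patients. No other visible provision turns a harm, or a count of harms, into a required pause.

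The study should be amended, because a safer procedure is available from AE data already collected. This is a gap in pre-specification. It is not evidence that patients are unmonitored or that the study cannot be stopped. The size of the benefit cannot be stated against the current plan, which sets no rule to compare with. Under the illustrative 3% rule at a true 20%, the chance of a pause runs from 46.9% to 91.2% depending on how many events are known at each review. The tolerable rate, the share of events known and a constant event risk across patients are all assumptions.

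**What to change.** Replace the interim sentence in Section 9 with a minimum rule:

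1. Review safety after 10, 20 and 30 treated patients, each once the latest counted patient has completed Visit 3. Treat no further patient until the review is documented. State which window governs: Section 4 allows 7 ± 4 days, while Appendix A gives days 4 to 10 with treatment on Day 1.
2. Count patients with at least one serious or severe AE judged related to the procedure or device. Show the count regardless of relatedness beside it.
3. Carry later events, including Month 3 MRI or CT findings, into the next review. Keep applying the 30-patient boundary count as events accrue in patients 31 to 40.
4. Before the first look, the sponsor fixes the tolerable rate and prints the boundary, for example 2/10, 3/20 and 4/30 for 3%. The looser 5% and 10% boundaries are illustrations only. Print the pause probabilities with a statement that they depend on accrual speed.
5. Pause treatment and notify the IRB and FDA if the boundary is reached, or after any related death.
6. State that the rule never limits earlier stopping under Section 6 or reporting under Section 7.3.

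The cost is a short amendment, two more tabulations, and up to three holds of 3 to 11 days plus review time, after which some screened patients may need repeat baseline assessments. The chance of an unneeded pause is about 3% to 6% over the three looks. It is higher once the count is carried to patient 40 (6.2% for the 3% rule), and the sponsor should print that figure too. Relatedness and severity remain the investigators' judgments.

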# 2. Study Objectives

# 2.1 Primary Objective

The primary objective of this investigation is to assess safety of genicular artery embolization (GAE) for knee osteoarthritis (OA) using Embozene particles.

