# 4. Study Design

This is a single-center, prospective, single arm investigational study to evaluate the safety of genicular artery embolization (GAE) for treatment of symptomatic knee osteoarthritis (OA). In addition, the improvement as part of efficacy will be reported. All subjects will have either failed or be intolerant to conservative management, and be ineligible for or refuse surgical intervention. Subjects will be considered enrolled in the study once they have provided informed consent and have been determined to meet all eligibility criteria. A total of 40 subjects will be enrolled in the single treatment arm of the study and will be followed for 12 months. The subjects will be stratified according to arthritis severity based on imaging, with 20 subjects allocated to mild-moderate arthritis based on x-ray (Kellgren-Lawrence x-ray grade 1-2), and with 20 subjects allocated to severe arthritis based on x-ray (Kellgren-Lawrence x-ray grade 3-4). The stratification will not be randomized, but each category will be limited to 20 patients.

The study will involve a screening period in which patient eligibility is determined. Once eligibility is confirmed, subjects will undergo GAE with Embozene microspheres (100 micron). Following treatment, subjects will return for follow-up visits at 1 week (± 4 days), 1 month (± 2 weeks), 3 months (± 2 weeks), 6 months (± 2 weeks), and 12 months (± 2 weeks) post-procedure. At these visits, subjects will complete the Western Ontario and McMaster Universities Osteoarthritis Index (WOMAC) score, and a visual analog scale (VAS) score, undergo a directed physical examination, and report any new adverse events (AEs). At 3 months of follow-up, subjects will also undergo knee x-ray. At the 12 month follow-up, subjects will also complete a patient-reported outcomes (PRO) and patient global impression of change (PGIC) questionnaire.

The primary objective of the study will be to assess safety via minor and major adverse events. Secondary objective will be improvement of OA symptoms as assessed by the WOMAC and VAS scores at each follow-up visit. Subjects will continue to be followed according to the institutional standard of care after they complete the 12-month study visit.

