#### Efficacy Analyses

The primary is the change in WOMAC before GAE to 12 months after GAE. All statistical tests and confidence intervals (CIs) will be two-sided with a nominal significance level of p < 0.05 (95% confidence). A linear mixed model (LMM) will be used to test for the mean change in WOMAC while adjusting for potential site-effects. The baseline and 12 month observations will be included in the model. The dependent variable will be the changes in WOMAC and the independent variables will be the WOMAC at baseline, baseline severity (moderate/severe arthritis), indicators of time (fixed effect  $\Delta$ ) and random intercepts for patient and site. The parameter  $\Delta$  corresponds to the mean change in WOMAC. A Wald-type test of  $\Delta = 0$  and 95% CI of  $\Delta$  will be calculated.

Secondary analyses will also include analyzing changes from baseline to other timepoints and between post-treatment timepoints using the same methods. The Kaplan-Meier curves will be used to analyze the time until WOMAC improvement is first observed (i.e. time to improvement). The Turnbull method will be used to estimate these curves while accounting for interval censoring (the clinical improvement event is only known to have occurred between the current and prior visit).

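### The safety precision stated for 40 patients (7.1% to 14.8%) is wrong: exact two-sided 95% limits give 8.8% to 16.7%, and the 83% power figure names no test

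*Combined protocol and SAP*

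**What the plan says.** Safety is the primary objective (Section 2.1). Section 4 sets the size: "A total of 40 subjects will be enrolled in the single treatment arm of the study". Half are to be Kellgren-Lawrence grade 1-2 and half grade 3-4.

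The Safety Analyses part of Section 9 justifies that number with two figures:

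- **Power.** "With 40 patients expected with the stratification of moderate and severe arthritis", it says, "we can achieve approximate 83% power to test the difference of 10% of the upper bound of a 95% CI", for an AE rate below 0.01% against 10%.
- **Precision.** For AE rates from 0% to 50%, "the difference between the upper bound of the 95% CI and the estimate AE rate ranges from 7.1% to 14.8" percent.

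It then gives the basis: "These calculations were based on exact binomial CIs, assuming no loss to follow up". The Efficacy Analyses part of the same section adds that "All statistical tests and confidence intervals (CIs) will be two-sided", at 95% confidence. Section 6 says of dropouts: "Patients who are withdrawn from the study for any reason will not be replaced".

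**The concern.** The precision sentence is fully specified: sample size, confidence level, interval method, range of rates and no dropout. It can be recomputed exactly, and neither printed end comes out.

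The trial has one arm, and its AE rates will be compared only qualitatively with the literature. The width of the interval is therefore the plan's real statement of what 40 patients can show about safety. A reader would conclude that zero events of a given type rules out rates above 7.1%, when 0/40 rules out only rates above 8.8%. Measured against the plan's own 10% reference rate, the margin falls from 10 − 7.1 = 2.9 points to 10 − 8.8 = 1.2 points.

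The power sentence has a different problem. It gives two rates but no null hypothesis, test, alpha or rejection rule, so nobody can verify the 83%.

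**Working it through.** **Inputs.** n = 40 (Sections 4 and 9); 95% confidence and exact binomial limits (Section 9, Safety Analyses); two-sided (Section 9, Efficacy Analyses, worded to cover all intervals); no loss to follow-up (Section 9); observed rates 0% to 50%, i.e. x = 0 to 20 events.

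**Formula.** The two-sided Clopper-Pearson upper limit U(x, n) is the 97.5th percentile of a Beta(x+1, n−x) distribution. The quantity in the plan is U(x, n) − x/n. At x = 0 it reduces to 1 − 0.025^(1/n).

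**Attempt to reproduce the plan's range at n = 40.**

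| Events | Estimate | Upper limit | Distance (points) |
|---|---|---|---|
| 0/40 | 0% | 8.81% | 8.81 |
| 4/40 | 10% | 23.66% | 13.66 |
| 6/40 | 15% | 29.84% | 14.84 |
| 7/40 | 17.5% | 32.78% | 15.28 |
| 15/40 | 37.5% | 54.20% | 16.70 (maximum) |
| 20/40 | 50% | 66.20% | 16.20 |

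The range is 8.8 to 16.7 points, against 7.1 to 14.8 printed: larger by 8.8 − 7.1 = 1.7 at the low end and 16.7 − 14.8 = 1.9 at the high end. Every count from 7/40 to 20/40 lies above the printed maximum.

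**Other intervals at n = 40.** None gives both printed ends.

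| Method | At 0/40 | Maximum | At 20/40 |
|---|---|---|---|
| Exact, one-sided 95% | 7.22 | 14.22 | 13.89 |
| Wilson | 8.76 | 15.49 | 14.80 |
| Agresti-Coull | 10.44 | 15.56 | 14.80 |
| Jeffreys | 6.05 | 15.45 | 15.04 |

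**Other sample sizes.** Among n = 5 to 300, with one- or two-sided exact limits, only n = 50 two-sided matches both ends: 7.11 at 0/50 and a maximum of 14.83 at 19/50. The documents mention no sample of 50, so this origin is an inference, and the error at n = 40 does not depend on it. Nor does the printed range apply within a severity stratum: at n = 20 the two-sided distance is 16.8 points at 0% and 22.8 at 50%.

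**Power.** With 40 patients and rates of 0.01% and 10%, the two exact one-sample readings are:

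- Null 0.01%, reject on at least one event: actual alpha 1 − 0.9999^40 = 0.4%; power at 10% = 1 − 0.9^40 = 98.5%.
- Null 10%, reject on zero events: actual alpha 0.9^40 = 1.5%; power at 0.01% = 0.9999^40 = 99.6%.

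Neither is near 83%. Two-group tests with 40 per group at 0.01% against 10%, two-sided 5%, give 53.6% (pooled z), 20.6% (Fisher) and 79.6% (arcsine).

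**Effect of dropout on the zero-event bound.** 1 − 0.025^(1/n) is 8.81% at n = 40, 9.74% at n = 36 and 10.003% at n = 35.

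**The case against.** Four points can be made for the plan.

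- **Sidedness.** The two-sided rule is printed under Efficacy Analyses, and the safety paragraph itself states none. Applying it to AE intervals is an inference, though the rule is worded to cover all of them. It matters at the low end, where the one-sided bound at 0/40 is 7.2%, only 0.1 point from the printed figure. But the one-sided maximum is 14.2%, so the printed pair still fails.
- **Method.** The Wilson distance at exactly 50% is 14.80, the printed upper figure. Its value at zero is 8.76, and the plan says exact, so this does not rescue the range either.
- **Power.** The sentence mentions stratification, which could point to strata of 20. A one-sample arcsine approximation at n = 20, for exactly 0% against 10% and two-sided 5%, gives 82.1%; a two-group arcsine test with 40 per group gives the same number. So a near match exists, but it is not an exact binomial method, it falls short of 83%, and the two-group reading needs 80 patients in two arms. The exact chance of at least one event among 20 at a 10% rate is 87.8%. What stands is a limit on the criticism: 83% does not follow from an exact one-sample test of 40, and beyond that it is unverifiable rather than shown to be wrong.
- **Impact.** The discrepancy is under two points, no decision rule uses it, and the plan openly assumes no loss to follow-up. All of that is true and keeps the consequence modest.

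**Conclusion.** The concern holds. On the plan's own inputs the distance from estimate to upper limit is 8.8% to 16.7%, not 7.1% to 14.8%. This rests on n = 40, Clopper-Pearson limits, two-sided 95% confidence and complete follow-up; of these only two-sidedness is not stated in the safety paragraph itself, and a one-sided reading does not reproduce the printed range.

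The 83% power figure cannot be checked as written and does not come from an exact one-sample test of 40 patients. No corrected power is offered, because the test is not identified. On the two exact readings above, 83% understates the power.

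The error lies in the planning statement and not in the results, since reported intervals will use observed counts. Zero events in 40 still excludes a 10% rate, so the sample size is not undermined. The margin is thin, however: with no replacement of withdrawn patients, zero events excludes 10% only if at least 36 patients are evaluable. Because these two figures are the only quantitative justification of the sample size for the primary objective, they should be corrected.

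**What to change.** In Section 9, Safety Analyses:

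1. Replace the printed range with: *8.8% (0/40) to 16.7% (15/40; 16.2% at an observed rate of 50%)*. State in the same place that the AE intervals are two-sided.
2. For the power sentence, either give the null hypothesis, test, alpha and rejection rule and correct the figure, or replace it with a precision statement such as: *With no events in 40 patients the exact two-sided 95% upper bound is 8.8%; the probability of seeing at least one event of a type whose true rate is 10% is 98.5%.*
3. Beside the no-dropout assumption, it would help to add that the zero-event bound is 9.7% with 36 evaluable patients and just over 10.0% with 35.

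The cost is a few sentences. The stated precision becomes slightly less favourable; no patients are added and the analysis does not change.
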